### 3.1.2. SECONDARY STUDY OUTCOMES

1. Incidence of adverse events (AE) and serious adverse events (SAEs) in children receiving LAIV:
  - AEs occurring up to 72 hours after LAIV.
  - SAEs unrelated to asthma symptoms with onset up to 72 hours after LAIV
  - Incidence of a 'significant exacerbation' in asthma, defined as:
    - i. At least 3 day course of oral steroids following an unscheduled contact with a healthcare professional; OR
    - ii. Unscheduled visit to an Emergency department or admission to hospital for treatment of asthma symptoms, requiring systemic corticosteroids
2. Incidence and extent of viral shedding in children and young people receiving LAIV during the 2016/17 influenza season, using quantitative analysis of consecutive nasal swabs obtained up to 10 days following LAIV. These data will be correlated with the incidence of adverse events related to asthma over the same time period.

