### 9.2 SAMPLE SIZE ESTIMATION

Sample size is based on the primary objective of comparing the proportion of participants who experience a significant change in asthma control, as measured by a change in at least 3 points *and* from  $\geq 20$  on the (C-)ACT (good control) to  $< 20$  (sub-optimal control) in each group (BTS  $\leq 3$  vs BTS 4/5), or vice versa. In the SNIFFLE-2 study, such a change (one way or the other) was seen in about 20% of children (10% worse, 10% better).

A sample of 400 children in each group will provide sufficient power (5% significance level, 80% power) to detect an improvement in 10% vs deterioration in 17.5%, allowing for 10% attrition. In SNIFFLE-2, follow-up at four weeks was 89%. If the proportion of participants with a change in ACT score is less than this, with only 5% improving and 10% getting worse, a sample size of about 420 would provide a similar level of power. This would represent a conservative assumption in the proportions changing. For comparing the average change pre to post vaccination in ACT score between the severe and non-severe groups, the standard deviation of change from SNIFFLE-2 was used (about 3 units). With a sample size of 400 in each group the detectable difference is 0.6 units between the groups (80% power, 5% significance).

Assuming that about 1% of participants experience a significant deterioration in asthma control (as defined in 3.1.2 above), then the 95% CI for a significant deterioration will be from 0.027% to 2.54%. If 0/400 are observed the upper 95% CI is 0.92%.

---

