## AGE 2-4 YEARS, $\geq 2$ EXACERBATIONS IN THE PAST YEAR AS DEFINED IN SECTION 9.1 .

### 9.3 STATISTICAL ANALYSIS PLAN

In brief, a per-protocol analysis will be completed for all individuals with at least one safety measurement. Proportions with AEs will be estimated with 95% CIs.

**For the primary outcome**, the change in TRACK or ACT score pre- and 4 weeks post LAIV will be assessed by McNemar's test for paired data. The minimum important difference (MID) for the ACT score is around 2 points in children and 3 points in adults, and 10 points for TRACK. For the purpose of this analysis, a change in ACT of at least 3 points, or 10 points for TRACK will be determined to be a significant change, where this results in an ACT score below 20 or TRACK score below 80 points.

**For secondary outcomes**, the incidence of reactions to LAIV (both immediate and delayed) and significant exacerbation in asthma will be estimated with 95% confidence intervals. Comparison to historical rates will be by Fisher's exact test.

Sub-group analyses will be performed using the following criteria:

- Age: 2-4, 5-11, 12-17 years
- Severity of respiratory symptoms: "severe" vs "non-severe"
- Children who have previously received influenza vaccine
- Children receiving high dose inhaled corticosteroids ( $\geq 800$  mcg/day beclomethasone dipropionate, or equivalent) vs those who are not. This cut-off will be applied to all participants age 6+ years.

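### Section 9.2 gives the lower 95% limit for a 1% deterioration rate as 0.027%; the exact limit for 4/400 is 0.27%, ten times higher

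*Combined protocol and SAP*

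**What the plan says.** Section 9.2 (Sample Size Estimation) closes with two sentences on precision. The first begins "Assuming that about 1% of participants experience a significant deterioration in asthma control", refers to Section 3.1.2 for the definition, and continues "then the 95% CI for a significant deterioration will be from 0.027% to 2.54" per cent. The second reads "If 0/400 are observed the upper 95% CI is 0.92" per cent. Neither names the interval method, and the first gives no denominator. Earlier in the same section the group size is given: "A sample of 400 children in each group will provide sufficient power".

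The definition in Section 3.1.2 is introduced as "Incidence of a 'significant exacerbation' in asthma, defined as". The event in Section 9.2 is therefore read here as the significant exacerbation, a listed secondary outcome. Section 9.3 plans to report it in the same form: "significant exacerbation in asthma will be estimated with 95% confidence intervals". The lower limit of 0.027% is not repeated anywhere else in the document.

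**The concern.** An interval around 1% that reaches down to 0.027% but only up to 2.54% is unusually lopsided. The upper limit is about 2.5 times the estimate, while the lower limit is the estimate divided by 37 (1/0.027 = 37). Four events in 400 cannot leave the lower side that uncertain, which suggests a decimal slip.

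These two sentences are the plan's only statement of precision for the significant exacerbation outcome. A reader who sets an observed 4/400 against a background rate would take from them that a true rate as low as 1 in 3,700 is still compatible with the data. Nothing else in the plan is built on that figure, so the correctness of the precision statement itself is what is at stake.

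**Working it through.** **Inputs, all from Section 9.2**

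- Assumed event rate: about 1%.
- Denominator: 400, from the 0/400 sentence and the stated group size. The count of 4 (1% × 400) is inferred; the plan does not print it.
- Confidence level: 95%, two-sided.
- Printed limits: 0.027% and 2.54% at the 1% rate; 0.92% for 0/400.

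**Step 1: reproduce the 0/400 limit.** The exact two-sided upper limit with no events solves (1 − p)^400 = 0.025:

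p = 1 − 0.025^(1/400) = 1 − exp(−3.6889/400) = 0.00918 = 0.918%.

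This rounds to the printed 0.92%. The one-sided 95% version, 1 − 0.05^(1/400), is 0.746% and does not match. The section is therefore using the two-sided exact method at n = 400.

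**Step 2: the same method at 4/400.** With x events in n, the Clopper-Pearson limits are beta quantiles:

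- lower = Beta(0.025; x, n − x + 1) = Beta(0.025; 4, 397) = 0.273%
- upper = Beta(0.975; x + 1, n − x) = Beta(0.975; 5, 396) = 2.540%

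The upper limit matches the printed 2.54%. The lower limit does not match: 0.2731/0.027 = 10.1.

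**Step 3: check against the definition of the limit.** The lower limit is the rate at which four or more events in 400 has probability 0.025. The upper limit is the rate at which four or fewer has that probability.

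| True rate | Expected events in 400 | Tail probability |
|---|---|---|
| 0.027% (printed lower) | 0.108 | P(X ≥ 4) = 0.000005 |
| 0.2731% (exact lower) | 1.09 | P(X ≥ 4) = 0.025 |
| 2.54% (printed upper) | 10.16 | P(X ≤ 4) = 0.025 |

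The printed upper limit meets the definition. The printed lower limit misses it by a factor of several thousand.

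**Step 4: could another method explain 0.027%?**

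| Method | 4/400 | Upper limit, 0/400 |
|---|---|---|
| Printed | 0.027% to 2.54% | 0.92% |
| Exact (Clopper-Pearson) | 0.273% to 2.540% | 0.918% |
| Wald | 0.025% to 1.975% | 0% |
| Wilson | 0.390% to 2.543% | 0.951% |
| Agresti-Coull | 0.294% to 2.638% | 1.147% |
| Jeffreys | 0.339% to 2.360% | 0.626% |
| Exact Poisson | 0.272% to 2.560% | 0.922% |

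Only the exact binomial row agrees with both printed upper limits. Wald comes closest to the printed lower limit, but its value is 0.025%, its upper limit is 1.98%, and it gives a zero-width interval for 0/400.

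**Step 5: could another count or denominator explain it?** Other group or total sizes suggested by the plan give these exact intervals:

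- 4/420: 0.26% to 2.42%
- 4/360 (400 less 10% attrition): 0.30% to 2.82%
- 8/800: 0.43% to 1.96%
- 8/840: 0.41% to 1.87%

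None has an upper limit of 2.54%. A search over 1 to 14 events and n = 20 to 1,000 found one exact interval that rounds to 0.27% to 2.54%, namely 4/400. Over the same range, no exact, Wald, Wilson, Agresti-Coull or Jeffreys interval rounds to 0.027% to 2.54%.

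**Size of the error in plain terms.** 1/0.00027 = 3,704, and 1/0.002731 = 366.

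**The case against.** The strongest case against raising this is that it changes no decision. The limit is illustrative, the trial will report intervals from its observed data, and for a safety event the upper limits matter most; both are right. The slip also widens the interval, so it does not exaggerate what the study can show. All of this is accepted, and it is why the point is minor. It remains a wrong figure in the section that states the trial's precision.

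A second objection is that count, denominator and method are all inferred, and that 2.54% alone does not identify the exact method: Wilson at 4/400 also has an upper limit of 2.54%, and its lower limit would be 0.39%, not 0.27%. This is a fair challenge, but the next sentence answers it. Wilson gives 0.95% for 0/400, whereas the plan prints 0.92%, which is the exact value. What stands is that the reader has to work this out, so the method belongs in the text.

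Third, Section 9.2 speaks of a deterioration in control while Section 3.1.2 defines an exacerbation. The cross-reference makes the reading used here reasonable, and the arithmetic does not depend on it. Only the description of these sentences as the precision statement for that secondary outcome does.

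Finally, a zero introduced when the text was extracted cannot be strictly excluded. Nothing points to it: the figure stands in ordinary running prose.

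**Conclusion.** The concern holds. The lower limit in Section 9.2 should be 0.27%, not 0.027%: about 1 in 366 instead of about 1 in 3,700. The limits of 2.54% and 0.92% are correct.

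The conclusion assumes that the 1% rate means 4 events in 400 and that the interval is the two-sided exact binomial one. Both are inferred, but the two correct limits in the same section support them, and none of the alternatives tried restores 0.027%. A misplaced decimal point is the likely cause.

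Severity is minor. The sample size in Section 9.2, the stopping criteria in Section 8.6 and the analyses in Section 9.3 do not depend on this limit.

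**What to change.** In Section 9.2, replace 0.027% with 0.27%. In the same sentence, state that the interval is the exact (Clopper-Pearson) 95% interval for 4/400, and have the authors confirm that 400 means each severity group. It would also help to use the Section 3.1.2 term, significant exacerbation, if that is the event meant.

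The cost is one corrected figure and a few words of text. Sample size, stopping rules and analyses stay as they are.

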#### POPULATION TO BE ANALYSED

CHILDREN AGED 2-18 YEARS (INCLUSIVE) WITH A PHYSICIAN-DIAGNOSIS OF ASTHMA OR RECURRENT WHEEZING, REQUIRING REGULAR MAINTENANCE THERAPY OR, IF

## AGE 2-4 YEARS, $\geq 2$ EXACERBATIONS IN THE PAST YEAR AS DEFINED IN SECTION 9.1 .

### 9.3 STATISTICAL ANALYSIS PLAN

In brief, a per-protocol analysis will be completed for all individuals with at least one safety measurement. Proportions with AEs will be estimated with 95% CIs.

**For the primary outcome**, the change in TRACK or ACT score pre- and 4 weeks post LAIV will be assessed by McNemar's test for paired data. The minimum important difference (MID) for the ACT score is around 2 points in children and 3 points in adults, and 10 points for TRACK. For the purpose of this analysis, a change in ACT of at least 3 points, or 10 points for TRACK will be determined to be a significant change, where this results in an ACT score below 20 or TRACK score below 80 points.

**For secondary outcomes**, the incidence of reactions to LAIV (both immediate and delayed) and significant exacerbation in asthma will be estimated with 95% confidence intervals. Comparison to historical rates will be by Fisher's exact test.

Sub-group analyses will be performed using the following criteria:

- Age: 2-4, 5-11, 12-17 years
- Severity of respiratory symptoms: "severe" vs "non-severe"
- Children who have previously received influenza vaccine
- Children receiving high dose inhaled corticosteroids ( $\geq 800$  mcg/day beclomethasone dipropionate, or equivalent) vs those who are not. This cut-off will be applied to all participants age 6+ years.

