## 1. INTRODUCTION

### 1.1 BACKGROUND

Data collected during previous pandemic situations, as well as mathematical modelling of mixing patterns and infectivity, have shown that children serve as the most important reservoir for influenza infection and transmission.

Vaccinating children may therefore provide the most effective method for interrupting the chain of transmission and so achieving disease control. This was recognised by the Joint Committee for Vaccination and Immunisation (JCVI), who at its meeting in June 2012 recommended the annual vaccination of all children aged 2-16 years of age with the live attenuated influenza vaccine (LAIV). LAIV has been shown to be more effective in this age group than the inactivated trivalent influenza vaccine (TIV) which, though recommended for annual vaccination children with specific risk factors, has variable efficacy in young children depending on the match between vaccine and circulating strains.

The safety of LAIV in non-atopic children has been demonstrated in a number of published studies, and to date over 1 million doses have been given. However, LAIV contains very small amounts of egg protein (ovalbumin) and until recently has been contraindicated in children with egg allergy. The SNIFFLE-1 and SNIFFLE-2 studies, commissioned by Public Health England, demonstrated the safety of LAIV in children with egg allergy. A total of 1237 doses were administered in 887 children, with no systemic allergic or anaphylactic reactions observed. Administration of LAIV in children with a history of asthma or recurrent wheezing did not affect asthma control. This is important, because USA guidelines currently recommend against the use of LAIV in children with a history of wheezing in the preceding 12 months, although the evidence for this recommendation is poor. However, due to the small numbers of children on high-dose inhaled corticosteroids (BTS/SIGN step 4+ treatment), only limited conclusions could be drawn regarding the safety of LAIV in children with “severe asthma” (defined as BTS/SIGN step 4+ therapy).

We now wish to assess the safety of LAIV in children with asthma, including those children with “severe asthma” or “difficult-to-control” symptoms, to increase the safety data in this sub-population.

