## 1.3 STUDY RATIONALE & JUSTIFICATION

The JCVI has recommended annual influenza vaccination for all children 2-16 years of age. The programme commenced using Fluenz in the 2013/2014 influenza season, was initially restricted to children under 4 years of age for logistic reasons, but is subsequently being expanded over the next few years to include all children under 16 years.

To date, there are only limited data available regarding the safety of LAIV in children with “severe” asthma requiring high dose inhaled corticosteroid therapy (or more intensive treatment). In the SNIFFLE-1 and -2 studies, only 49 children were included requiring BTS Step 4+ treatment. This lack of data is reflected in the current guidance from Department of Health:

“There is limited safety data on children who are currently taking a high dose of an inhaled steroid – Budesonide >800 mcg/day or equivalent (e.g. Fluticasone >500 mcgs/day) – such children should only be given LAIV on the advice of their specialist.”

This study will enrol 840 children with a history of asthma or recurrent wheezing (target 420 at BTS 4+ or greater, the remaining 420 participants at lesser levels of treatment), to obtain further safety data relating to the administration of LAIV in this group of children and thus inform UK guidance with regard to LAIV.

The study includes an assessment of influenza virus shedding following LAIV. Though efficacy of the vaccine has been maintained in the first few years of LAIV use in the UK, this is not so in the USA where it has been used for the last decade. The unique cohort included in this study provide an opportunity to assess viral shedding in the period immediately after vaccination, through parental collection of nasal swabs at three time points in the week following vaccination, which will be posted in prepaid bags directly to the testing laboratory at PHE Colindale. This will likely be 24 hours, 72 hours and 6 days after vaccination but these time points will be confirmed nearer the start of the study based on international data which is being gathered and published now. There may be a correlation between vaccine shedding and adverse events following vaccination. The data will also help inform as to whether there is a link between vaccine shedding and previous exposure to influenza vaccines including previous LAIV, an issue which might explain the apparent lower efficacy of LAIV in the USA compared to UK and Finland.

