## 4.1 RECRUITMENT

Subjects will be recruited through 2 routes:

1. Children currently managed within the existing paediatric services at participating study sites. Recruitment will be via publicity (posters, flyers), email and postal mailing (with an option for a follow-up contact by post, email or telephone\* where there is no response to the initial invite).
2. Children who received the LAIV vaccine in 2014-16 as part of the SNIFFLE studies, who have a diagnosis of asthma or recurrent wheezing and are currently cared for by the clinical team at participating study sites. Families will receive a separate letter of invitation (by post or email), from their clinical team.

\*Telephone calling will only take place where the child/family is already under the care of the local clinical team, and the clinician thus has an established relationship with the family.

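### The historical comparison uses a crude Fisher test on a cohort set at 50% BTS 4+, so severity mix alone can create an apparent excess of exacerbations

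*Combined protocol and SAP*

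**What the plan says.** Section 9.3 states that for secondary outcomes "the incidence of reactions to LAIV (both immediate and delayed) and significant exacerbation in asthma will be estimated with 95% confidence intervals", and then: "Comparison to historical rates will be by Fisher's exact test". That is the whole method. The plan does not say which rates are meant, and it does not mention stratification, adjustment, matching or restriction.

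Section 1.3 sets the severity mix of this cohort ("target 420 at BTS 4+ or greater, the remaining 420 participants at lesser levels of treatment") and says of SNIFFLE-1 and -2 that "only 49 children were included requiring BTS Step 4+ treatment". Section 1.1 gives the size of those studies ("A total of 1237 doses were administered in 887 children") and their population: they "demonstrated the safety of LAIV in children with egg allergy".

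Section 4.1 lists a second recruitment route: "Children who received the LAIV vaccine in 2014-16 as part of the SNIFFLE studies", provided that they have asthma or recurrent wheeze.

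Section 9.3 also lists severe versus non-severe as a subgroup analysis, but does not link it to the historical comparison.

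**The concern.** Fisher's test on a single 2x2 table compares two overall rates. If the two groups differ in the share of severe children, and severe children have more events, the overall rates differ even when children of equal severity do equally well. Here the severity share is fixed by design at a level far above that of the earlier SNIFFLE studies. Those are the only earlier LAIV cohorts whose figures the protocol uses for planning (sections 1.1, 1.3 and 9.2).

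Significant exacerbation is the outcome most exposed, because a severity gradient is most plausible there. The study is meant to inform UK guidance on LAIV in children on intensive asthma treatment. A significant rise over past rates could be taken as a finding about this season or this cohort when it reflects only who was enrolled.

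**Working it through.** **The plan's own figures.** The documents give no figure for the historical comparison. The nearest is in section 9.2: "Assuming that about 1% of participants experience a significant deterioration in asthma control". For 4/400, exact (Clopper-Pearson) limits are 0.27% to 2.54%. The upper limit matches the plan; its printed lower limit of 0.027% looks like a decimal slip. For 0/400 the upper limit is 0.92%, as stated. The 1% rate is used below as the overall rate in this cohort.

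**Inputs from the documents**
- Current severe share: 420/840 = 50%.
- Evaluable children: 840 x 0.90 = 756 (10% attrition, section 9.2), so 378 per severity group.
- Historical severe share s: 49/887 = 0.055.

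**Assumptions, not in the documents**
- The comparator is SNIFFLE-1/-2.
- If restricted to children with asthma, the denominator is 400, giving s = 49/400 = 0.1225.
- Severe children have k = 2 to 3 times the non-severe rate.
- The test is two-sided at 5%. Section 9.2 states 5% for the sample size; no level is stated for this comparison.
- Rates within each severity level are the same in both datasets, so there is no true difference.

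**Step 1: distortion of the rate ratio.** Current rate / historical rate = [1 + 0.5(k - 1)] / [1 + s(k - 1)].
- 400 historical: k = 2 gives 1.5/1.1225 = 1.34; k = 3 gives 2/1.245 = 1.61.
- 887 historical: k = 2 gives 1.5/1.055 = 1.42; k = 3 gives 2/1.110 = 1.80.

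**Step 2: stratum rates at 1% overall.** Non-severe rate = 1% / [(1 + k)/2]. For k = 2 this is 0.67%, with 1.33% in severe children. For k = 3 it is 0.50%, with 1.50% in severe children.

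**Step 3: probability of a false excess.** Current events are Bin(378, severe rate) + Bin(378, non-severe rate). Historical events are Bin(49, severe rate) + Bin(H - 49, non-severe rate), where H is the historical total. Exact enumeration gives the probability that two-sided Fisher p < 0.05 with the current rate higher:

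| Ratio k | H = 400 | H = 887 |
|---|---|---|
| 1.5 | 2.2% | 4.1% |
| 2 | 3.1% | 6.9% |
| 3 | 4.7% | 13.0% |

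The nominal upper tail is 2.5%. As a control with k = 1, the result stays between 1.3% and 2.2% in the 756-child setting (non-severe rate 1% or 5%). The inflation therefore comes from severity mix alone.

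**Step 4: sensitivity to the event rate.** If 1% is instead the non-severe rate, the overall rate is 1.5% (k = 2) or 2.0% (k = 3). The false-excess probability becomes 4.8%-11.1% with H = 400 and 9.9%-27.5% with H = 887.

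**Step 5: effect of stratifying.** A continuity-corrected Mantel-Haenszel test stratified by severity was simulated under the same null with 840 current children, non-severe rates of 1%-5%, ratios of 1-5 and H = 400 or 887. False excess was 0.6%-1.9% throughout.

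**Step 6: what stratifying can detect.** Power for an excess among severe children, 420 current versus 49 historical, by Fisher's test:
- 3% historical versus 6% current: 2%
- 3% versus 9%: 23%
- 5% versus 10%: 14%
- 10% versus 20%: 35%

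**The case against.** **The comparator is inferred.** This stands. If the historical rates come from elsewhere, the 49/887 arithmetic does not apply. But a plan that names no source cannot show that case mix is comparable, and the current cohort is half BTS 4+ whatever the source.

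**Safeguards exist.** The primary analysis is within-child (McNemar), and section 2.2 compares symptoms in the 4 weeks before and after LAIV. Between-study case mix biases neither, so a reader who inferred that the primary result is compromised would be wrong. Neither analysis protects the separate historical comparison. The listed severity subgroups could, but the plan does not say that the comparison is made within them.

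**The inflation is modest at the planned rate.** This stands for the 400-child case, which is arguably closer to like-for-like. A non-severe rate of 5% would give false excesses of up to about 92%, but it implies 7.5%-10% overall at ratios of 2-3. Nothing in the documents supports that against a planning value of about 1%.

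**Not every outcome depends on severity.** This also stands. The documents give no reason to think that allergic or other non-respiratory reactions are more frequent at BTS 4+, and for those severity mix causes no inflation.

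**Re-enrolment.** A reader might infer that children counted on both sides produce a false harm signal. The number re-enrolled is not given, and positive within-child correlation would generally make an independent-samples test conservative. The overlap breaks the test's independence assumption but is not shown to create an excess.

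**Conclusion.** The point holds for severity-related outcomes, chiefly significant exacerbation. At the planned 1% overall rate, with 756 evaluable children and a severe:non-severe ratio of 2-3, the crude test shows a false excess about 3%-5% of the time against 400 historical children and 7%-13% against 887, where 2.5% is nominal. Higher event rates make it worse. The size rests on three assumptions that the documents do not settle: SNIFFLE-1/-2 as comparator, the 400 denominator and the severity ratio.

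A reader might go further and say that the excess would be blamed on the vaccine. If SNIFFLE-1/-2 is the comparator, both sides received LAIV, so the contrast is between studies and cannot by itself be credited to LAIV. The defect is confounding in a secondary comparison. It is worth correcting before analysis but does not threaten the main result.

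**What to change.** Amend section 9.3 as follows.

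1. Name the historical source and restrict it to children with asthma or recurrent wheeze.
2. For exacerbation and other respiratory outcomes, replace the crude Fisher test with a comparison stratified by severity: an exact or Mantel-Haenszel common odds ratio with 95% CI, plus the rates in each stratum.
3. Define severity the same way in both datasets. Section 9.1 uses a different rule at ages 2-4 from that at 5 and over, so the historical BTS 4+ count may not map directly.
4. Count re-enrolled children on one side only.
5. Where the source cannot be split by severity, give rates with CIs and no test.

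Stratifying by age as well is not practical: 1% of 756 is about 8 events.

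The cost is SAP wording and obtaining severity for the historical children; this study needs no new data collection. The downside is very low power in the severe stratum, so the plan should call the comparison descriptive and say that absence of a difference there is not evidence of equal rates.
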